## Duration of symptoms:

- A focal or global neurological deficit  $\geq$  24 hours
- A focal or global neurological deficit  $<$  24 hours if available neuroimaging indicates a new intracranial or subarachnoid hemorrhage (hemorrhagic stroke) or central nervous system infarction (ischemic stroke) or
- The neurological deficit results in death

**II. TIA: duration of a focal or global neurological deficit ,24 h and neuroimaging does not demonstrate a new haemorrhage or infarct****Confirmation of the diagnosis by at least one of the following:**

- Neurologist or neurosurgical specialist, or
- Neuroimaging procedure (CT scan or brain MRI)
- Non-neurologist physician (if neurologist is not available)
- Clinical presentation alone\*\*\*

**Stroke types will be adjudicated as:**

**I. Ischemic:** an acute symptomatic episode of focal cerebral, spinal, or retinal dysfunction caused by an infarction of the central nervous system tissue

**II. Hemorrhagic:** an acute episode of focal or global cerebral or spinal dysfunction caused by intraparenchymal, intraventricular, or subarachnoid hemorrhage

**III. Undetermined:** if there is insufficient information to allow categorization as ischemic or hemorrhagic

**Stroke severity**

It is recognized that an assessment of stroke is incomplete without an appropriate measurement of the disability resulting from the stroke, hence, mRS closest to 90 days post event\*\* will be used to assess clinical disability.

- I. Disabling:** mRS score of  $\geq 2$  at 90 days (or the last available clinical visit with evaluable data) AND an increase in  $\geq 1$  mRS category from an individual's pre-stroke baseline
- II. Non-disabling:** mRS score of  $< 2$  at 90 days (or the last available clinical visit with evaluable data) or doesn't result in an increase in  $\geq 1$  mRS category from pre-stroke baseline

**TIA**

Acute episode of a focal or global neurological deficit fulfilling the following criteria:

1. Resulting in at least one of the following
  - Change in level of consciousness
  - Hemiplegia
  - Hemiparesis
  - Numbness
  - Sensory loss affecting one side of the body
  - Dysphasia or aphasia
  - Hemianopia
  - Amaurosis fugax
  - Other neurological signs or symptoms consistent with stroke
2. Duration of deficit could be one of the following:
  - A focal or global neurological deficit  $< 24$  hours
  - Any available neuroimaging does not demonstrate a new hemorrhage or infarct
3. No other readily identifiable non-stroke cause for the clinical presentation (e.g. brain tumor, trauma, infection, hypoglycemia, peripheral lesion, pharmacological influences) to be determined by or in conjunction with a neurologist.\*

**Notes:**

\*Patients with non-focal global encephalopathy will not be reported as a stroke without unequivocal evidence based upon neuroimaging studies.

\*\*Evaluation of stroke between 30 and 90 days is acceptable if 90-day follow-up not available

\*\*\* If a stroke is reported without evidence of confirmation of the diagnosis by one of these methods, the event may still be considered a stroke on the basis of the clinical presentation alone.

**APPENDIX C: ABBREVIATIONS AND ACRONYMS**

Abbreviation/Acronym	Definition
6MWT	6 Minute Walk Test
ACC	American College of Cardiology
ACT	Activated Clotting Time
ADL	Activities of daily living
AE	Adverse Event
AHA	American Heart Association
AKI	Acute Kidney Injury
ALP	Alkaline phosphatase
ALT	Alanine transaminase
AST	Aspartate aminotransferase
CABG	Coronary Artery Bypass Graft
CEC	Clinical Events Committee
CFR	Code of Federal Regulations
CHF	Congestive Heart Failure
CIB	Clinical Investigator's Brochure
CIP	Clinical Investigational Plan
CMR	Cardiovascular Magnetic Resonance
COPD	Chronic obstructive pulmonary disease
CRF	Case Report Form
CT	Computed Tomography
CTA	Clinical Trial Agreement
CV	Cardiovascular
DAPT	Dual anti-platelet therapy
DSMB	Data Safety Monitoring Board
DVT	Deep vein thrombosis
ECG	Electrocardiogram
eCRF	Electronic case report form
EDC	Electronic data capture
EF	Ejection Fraction
eGFR	Estimated glomerular filtration rate
EROA	Effective regurgitant orifice area
FDA	Food and Drug Administration
GCP	Good Clinical Practice
GGT	Gamma-Glutamyl Transferase

PROPRIETARY DATA: THIS DOCUMENT CONTAINS CONFIDENTIAL AND PROPRIETARY INFORMATION OF EDWARDS LIFESCIENCES, LLC. IT MUST NOT BE REPRODUCED OR DISCLOSED TO THIRD PARTIES WITHOUT PRIOR WRITTEN PERMISSION OF EDWARDS LIFESCIENCES, LLC. DOC-0077299 Rev: B – Clinical Investigation Plan Template; This form is required by DOC-0089089; Edwards Lifesciences, Edwards, the stylized E logo, and PASCAL Transcatheter Valve Repair System are trademarks of Edwards Lifesciences Corporation.

Abbreviation/Acronym	Definition
GI	Gastrointestinal
HF	Heart Failure
Hgb	Hemoglobin
ICF	Informed consent form
ICU	Intensive care unit
IFU	Instructions For Use
INR	International normalized ratio
IRB	Institutional Review Board
ISO	International Standardization Organization
ITT	Intention-to-treat
IVC	Inferior vena cava
KCCQ	Kansas City Cardiomyopathy Questionnaire
LV	Left ventricle
LVEF	Left ventricular ejection fraction
MAE	Major Adverse Event
MI	Myocardial Infarction
MR	Mitral Regurgitation
mRS	Modified Rankin Scale
MSAE	Major Serious Adverse Event
MSCT	Multi-slice computed tomography
MV	Mitral Valve
MVARC	Mitral Valve Academic Research Consortium
NYHA	New York Heart Association
PASP	Pulmonary Artery Systolic Pressure
PHTN	Pulmonary hypertension
PP	Per-protocol
QOL	Quality of Life
RA	Right atrium
RV	Right ventricle
SAE	Serious Adverse Event
SLDA	Single leaflet device attachment
STS	Society of Thoracic Surgeons
TEE	Transesophageal echocardiography
TIA	Transient Ischemic Attack
TMVr	Transcatheter Mitral Valve Repair
TMVR	Transcatheter Mitral Valve Replacement

Abbreviation/Acronym	Definition
TR	Tricuspid Regurgitation
TTE	Transthoracic Echocardiography
TTVr	Transcatheter tricuspid valve repair
TTVR	Transcatheter tricuspid valve replacement
TV	Tricuspid valve
UADE	Unanticipated adverse device effect
VC	Vena contracta

10. REFERENCES24

11. PEER REVIEW REQUEST, PER SAP INSTRUCTION (DOC-0089205)24

12. APPENDIX25

GLOSSARY OF TERMS

The following abbreviations are used throughout the document and shall not be defined elsewhere:

Abbreviation/Acronym	Definition
6MWT	6 Minute Walk Test
ACC	American College of Cardiology
ACT	Activated Clotting Time
ADL	Activities of daily living
AE	Adverse Event
AHA	American Heart Association
AKI	Acute Kidney Injury
ALP	Alkaline phosphatase
ALT	Alanine transaminase
AST	Aspartate aminotransferase
CABG	Coronary Artery Bypass Graft
CEC	Clinical Events Committee
CFR	Code of Federal Regulations
CHF	Congestive Heart Failure
CIB	Clinical Investigator’s Brochure
CIP	Clinical Investigational Plan

THIS DOCUMENT CONTAINS CONFIDENTIAL AND PROPRIETARY INFORMATION OF EDWARDS LIFESCIENCES, LLC. IT MUST NOT BE REPRODUCED OR DISCLOSED TO THIRD PARTIES WITHOUT PRIOR WRITTEN PERMISSION OF EDWARDS LIFESCIENCES, LLC.  

Revision Date: January 22, 2019

Rev

For Use Only by
Affiliates of
Edwards
Lifesciences

Page 5 of 25

Title

Statistical Analysis Plan for Edwards CLASP TR EFS

CMR	Cardiovascular Magnetic Resonance
COPD	Chronic obstructive pulmonary disease
CRF	Case Report Form
CT	Computed Tomography
CTA	Clinical Trial Agreement
CV	Cardiovascular
DAPT	Dual anti-platelet therapy
DSMB	Data Safety Monitoring Board
DVT	Deep vein thrombosis
ECG	Electrocardiogram
eCRF	Electronic case report form
EDC	Electronic data capture
EF	Ejection Fraction
EFS	Early Feasibility Study
eGFR	Estimated glomerular filtration rate
EROA	Effective regurgitant orifice area
FDA	Food and Drug Administration
GCP	Good Clinical Practice
GGT	Gamma-Glutamyl Transferase
GI	Gastrointestinal
HF	Heart Failure
Hgb	Hemoglobin
ICF	Informed consent form
ICU	Intensive care unit
IFU	Instructions For Use
INR	International normalized ratio
IRB	Institutional Review Board
ISO	International Standardization Organization
ITT	Intention-to-treat
IVC	Inferior vena cava
KCCQ	Kansas City Cardiomyopathy Questionnaire
LV	Left ventricle
LVEF	Left ventricular ejection fraction

Revision Date: January 22, 2019

Rev

For Use Only by
Affiliates of
Edwards
Lifesciences

Page 6 of 25

Title

Statistical Analysis Plan for Edwards CLASP TR EFS

MAE	Major Adverse Event
MI	Myocardial Infarction
MR	Mitral Regurgitation
mRS	Modified Rankin Scale
MSAE	Major Serious Adverse Event
MSCT	Multi-slice computed tomography
NAV	Mitral Valve
MVARC	Mitral Valve Academic Research Consortium
NYHA	New York Heart Association
PASP	Pulmonary Artery Systolic Pressure
PHTN	Pulmonary hypertension
PP	Per-protocol
QOL	Quality of Life
RA	Right atrium
RV	Right ventricle
SAE	Serious Adverse Event
SLDA	Single leaflet device attachment
STS	Society of Thoracic Surgeons
TEE	Transesophageal echocardiography
TIA	Transient Ischemic Attack
TMVr	Transcatheter Mitral Valve Repair
TMVR	Transcatheter Mitral Valve Replacement
TR	Tricuspid Regurgitation
TTE	Transthoracic Echocardiography
TTVr	Transcatheter tricuspid valve repair
TTVR	Transcatheter tricuspid valve replacement
TV	Tricuspid valve
UADE	Unanticipated adverse device effect
VC	Vena contracta

	Revision Date: January 22, 2019		Rev	For Use Only by Affiliates of Edwards Lifesciences	Page 7 of 25
	Title	Statistical Analysis Plan for Edwards CLASP TR EFS			

1. INTRODUCTION

The statistical analysis plan (SAP) specifies the statistical methods to be implemented for the analysis of data collected within the scope of Edwards Lifesciences’s Clinical Protocol Study # 2018-10, “Edwards PASCAL Transcatheter Valve Repair System in Tricuspid Regurgitation (CLASP TR) Early Feasibility Study ” version A and provides detailed instructions as to how each analysis will be performed.

2. STUDY DESIGN

2.1 Study Objectives

The objectives of this early feasibility study are to:

- Evaluate the safety and performance of the PASCAL System
- Provide guidance for future clinical study designs utilizing the PASCAL System
- Provide guidance for future PASCAL System developments

2.2 Overall Study Design and Plan

This is a prospective, single arm, multi-center, early feasibility study designed to evaluate the safety and performance of the PASCAL System in the treatment of symptomatic severe regurgitation (TR).

 Edwards Lifesciences	Revision Date: January 22, 2019		Rev	 For Use Only by Affiliates of Edwards Lifesciences	Page 8 of 25
	Title	Statistical Analysis Plan for Edwards CLASP TR EFS			

A total of 15 patients will be enrolled in the study at up to 8 investigational sites in the US. All enrolled study patients will be assessed for clinical follow-up at the following intervals: discharge, 30 days, 6 months, 1 year and annually for 5 years post implant procedure.

A description of each study visit and required study procedures is included in the clinical protocol's Section 8, Procedures and Methods. In addition, a summary of required procedures is listed in Table 11, Schedule of Assessments of the clinical protocol.

3. STUDY ENDPOINTS

3.1 Safety Endpoint:

Safety will be analyzed as a composite endpoint of Major Adverse Events (MAEs) at 30 days which includes cardiovascular mortality, myocardial infarction (MI), stroke, renal complications requiring unplanned dialysis or renal replacement therapy, severe bleeding (includes fatal, life-threatening, extensive, or major bleeding, as defined by MVARC), unplanned or emergency re-intervention (either percutaneous or surgical) related to the device and major access site and vascular complications requiring intervention.

3.2 Performance Endpoints

3.2.1 Device Success

Device is deployed as intended and the delivery system is successfully retrieved as intended at the time of the patient's exit from the cardiac catheterization laboratory. Per device analysis.

3.2.2 Procedural Success

	Revision Date: January 22, 2019		Rev	For Use Only by Affiliates of Edwards Lifesciences	Page 9 of 25
	Title		Statistical Analysis Plan for Edwards CLASP TR EFS		

Device success with evidence of a reduction in TR grade by at least one grade (scale: none/trace, mild, moderate, severe, massive, torrential) at end of procedure, and without the need for a surgical or percutaneous intervention prior to hospital discharge. Per patient analysis.

3.2.3 Clinical Success

Procedural success without MAEs at 30 days. Per patient analysis.

3.3 Echocardiographic, Clinical, and Functional Endpoints and Parameters

3.3.1 Echocardiographic Endpoints and Parameters

A. Reduction in TR severity (assessed by TR grade and quantitative measures) as assessed by TEE pre- and post-implant in the procedure room.

Additional echocardiographic parameters will be compared to baseline:

- B. TTE parameters assessed at baseline, discharge, 30 days, 6 months, 1 year and annually until 5 years post procedure.
 - 1. TR grade
 - 2. Vena Contracta (2D)
 - 3. EROA (PISA/2D or 3D/3D color Doppler)
 - 4. Regurgitant volume
 - 5. Tricuspid annular dimensions
 - 6. TV inflow gradient

 Edwards	Revision Date: January 22, 2019		Rev	 For Use Only by Affiliates of Edwards Lifesciences	Page 10 of 25
	Title	Statistical Analysis Plan for Edwards CLASP TR EFS			

7. Cardiac output
8. Right ventricle dimensions
9. Right atrium volume
10. Left ventricular Ejection Fraction
11. Inferior Vena Cava dimensions/respiratory variations
12. Hepatic vein flow reversal
13. Pulmonary artery pressure (mean)
14. Right ventricular function

3.3.2 Clinical and Functional Endpoints and Parameters

Clinical and functional endpoints-assessed at baseline and at various time points, depending on the parameter (see Clinical Protocol Version A, Table 11)

- A. All-cause mortality
- B. Heart Failure Hospitalization
- C. Unplanned or emergency re-intervention (either percutaneous or surgical) related to the device
- D. Volume overload assessed by serial measurements of:
 1. Body weight
 2. Edema assessment (1+ to 4+)
 3. Ankle circumference measurement

 Edwards	Revision Date: January 22, 2019		Rev	For Use Only by Affiliates of Edwards Lifesciences	Page 11 of 25
	Title	Statistical Analysis Plan for Edwards CLASP TR EFS			

4. Patient edema questionnaire.

E. Quality of Life and Functional status assessed by:

1. NYHA Classification
2. 6-Minute Walk Test (6MWT)
3. KCCQ
4. Short Form Health Survey (SF-36)

Clinical and Functional Parameters

- A. Baseline Canadian Study of Health and Aging (CSHA) Clinical Frailty Scale
- B. Baseline Katz Index of Independence in Activities of Daily Living (Katz ADL)
- C. Baseline Patient Preference Survey
- D. Electronic Diary (eDiary): Administered via a handheld device as follows:
 1. Baseline: Question(s) will be administered daily for a minimum of 2 weeks before the index procedure and then paused at time of admission for index procedure.
 2. Post discharge: Starting post discharge, question(s) will be administered daily for 7 days, every other week, to the 12-month follow-up visit.
 3. 12-month follow-up visit: Starting at the 12-month follow-up visit, question(s) will be administered daily for a week, up to 7 days.
- E. Activity Monitoring*: Administered via a wearable monitor as follows:
 1. Baseline: Activity monitoring will occur for a minimum of 2 weeks before the index procedure and then paused at time of admission for index procedure
 2. 30 days post discharge

 Edwards	Revision Date: January 22, 2019		Rev	 For Use Only by Affiliates of Edwards Lifesciences	Page 12 of 25
	Title		Statistical Analysis Plan for Edwards CLASP TR EFS		

3. 2 weeks at 3 months, 6 months, 9 months, and 12 months post index procedure.
- F. General Clinical and Laboratory Parameters assessed by:
1. Creatinine, BUN, uric acid, and eGFR
 2. Liver Panel (Albumin, Bilirubin, ALP, ALT, AST, GGT)
 - G. Diuretic medications and doses (No change in diuretics are allowed for at least 3 months post procedure unless patient presents with severe hypotension.)

3.3.3 Additional Safety Assessments

In addition to the above endpoints and parameters, a listing of all the AEs and SAEs for the entire study population will be provided.

4. ANALYSIS POPULATIONS

The analysis cohorts are defined below:

4.1 Intention-to-Treat (ITT) Population

The intention-to-treat (ITT) population includes all patients who signed informed consent, met eligibility criteria, and in whom the study procedure has been attempted (i.e. skin incision to introduce the PASCAL System).

The ITT population will be used for performance endpoints and safety analysis.

4.2 As-Treated (Implanted) Population

 Edwards	Revision Date: January 22, 2019		Rev	For Use Only by Affiliates of Edwards Lifesciences	Page 13 of 25
	Title	Statistical Analysis Plan for Edwards CLASP TR EFS			

The as-treated (implanted) population is a subset of ITT population and includes all patients in whom the study device is implanted and remains in position at the time of the patient's exit from the procedure room.

The as-treated (implanted) population will be the primary analysis population for performance and additional safety assessment.

4.3 Per-Protocol (PP) Population

The per-protocol (PP) population is a subset of as-treated (implanted) population in whom there are no major inclusion/exclusion criteria-related deviations.

Additional analyses of performance and safety data using the PP population will be performed if it is clinically meaningful in addition to the as-treated analysis.

5. DEFINITIONS

5.1 Analysis Dates

5.1.1 Study Start Date

For a patient who has the study implant procedure attempted, the study start date is defined as the study implant procedure date (day 0).

5.1.2 Treatment Start Date

The treatment start date is defined as the study implant procedure date (day 0).

5.1.3 Last Information Date

 Edwards Lifesciences	Revision Date: January 22, 2019		Rev	For Use Only by Affiliates of Edwards Lifesciences	Page 14 of 25
	Title		Statistical Analysis Plan for Edwards CLASP TR EFS		

The last information date is defined as the latest date assessed with any available information concerning the patient (e.g., most recent date out of: baseline assessment, procedure, discharge, all follow-up visits, laboratory tests, and adverse events). Last information date is used as the censor date for survival analyses.

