## 7.4 Study Exit Criteria and Procedures

The reason for study exit will be documented on the appropriate case report forms and in the medical records for each patient who exits the study.

Patients may exit the study for any of the following reasons:

- Screen Failure
- Study Device Attempted But Not Implanted
  - Enrolled patients for whom the implant procedure was prematurely aborted (e.g., entered procedure room and anesthesia induced, but study procedure not attempted (i.e. skin incision to introduce the PASCAL System) or TTVr procedure attempted but did not receive a study device, will be followed for 30 days for safety evaluations only or until resolution of any adverse events related to the implant procedure and then exited from the study.
- Study Device Re-intervention/Explant
  - Patients who have a surgical re-intervention where the device is explanted will be followed for 30 days post-re-intervention for safety evaluations only or until resolution of any adverse events related to the re-intervention and then exited from the study. Patients who have a percutaneous re-intervention where the study device remains in place will continue to be followed for the duration of the study.
- Completion per Protocol
- Withdrawal
  - Patient Withdrawal: The patient may voluntarily withdraw from the clinical study at any time, without penalty or loss of benefits to which they are otherwise entitled.
  - Physician Withdrawal: The Investigator also has the right to withdraw a patient if s/he feels it is in the best interest of the patient to do so.
- Death
- Lost to Follow-up
  - If a patient cannot be reached for a follow-up visit, the Investigator will document the contact efforts made to the patient and/or effort to obtain hospital records in the appropriate electronic case report form. If the patient cannot be reached in any way, or misses a visit, the patient will be considered “unable to contact” for that time interval. After three (3) documented unsuccessful attempts to make contact prove unsuccessful, a certified letter will

be sent to the patient's residence. If there is no response after the certified letter is sent, the patient will be considered "lost to follow-up".

- For patients who are lost to follow-up or withdraw early, Sponsor may request the site to search the Social Security Death Index and/or other death registries and may request the site to obtain the death certificate, if applicable.

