## 11.2 AE Reporting Requirements

The Investigator will report all adverse events to the Sponsor as soon as possible, but no later than 10 working days after the Investigator first learns of the event.

Each adverse event must be reported on a separate AE CRF. In the event that the EDC system is not in service or otherwise not accessible, the Sponsor must be notified by email [REDACTED]. The AE CRF should be completed as soon as possible thereafter.

At the time of initial notification, the following minimal information must be provided:

- Study site number
- Patient ID number
- Site's awareness date
- AE description
- Causal relationship to device and implant procedure, if known

The site will provide the Sponsor copies of relevant supporting source documentation (e.g. admission H&P, implant procedure report, discharge summary, echocardiogram and laboratory results) for all adverse events requiring CEC adjudication (at a minimum, safety endpoints) and those events determined by the Sponsor to require additional investigation.

Adverse events must be followed until resolution, the patient is lost to follow-up, the patient has withdrawn consent, or the adverse event is otherwise explained.

The Investigator will inform their IRB and FDA of adverse events in accordance with the relevant local and regional regulatory requirements.

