6. STATISTICAL ANALYSIS

6.1 General Conventions

- For continuous variables, data will be summarized using the number of observations, mean, median, standard deviation, minimum, maximum, and 95% confidence intervals (based on normal distribution) per table shells. Nonparametric techniques may be used if the data

 Edwards Lifesciences	Revision Date: January 22, 2019		Rev 	For Use Only by Affiliates of Edwards Lifesciences	Page 15 of 25
	Title	Statistical Analysis Plan for Edwards CLASP TR EFS			

does not meet the assumptions of parametric tests.

- For categorical variables, data will be summarized using the number of observations, percentage, and 95% Clopper-Pearson confidence intervals per table shells. In general, the denominator for the percentage calculation will be based on total number of patients with evaluable data for a specified time point unless otherwise specified. Patients with missing data will be excluded from the denominator.
- For time-to-event variables, survival analysis will be used to analyze the data. Summaries will include the number of patients at risk, and number of patients with the event. Patients without events will be censored at their last known event-free time point. If this event-free time point occurs after the analysis time point, the days to event variable will be set equal to the analysis time point so that the patient will be included in the analysis. For patients who did not have an event or early withdrawal and have not yet completed the analysis visit, they will be censored at their last information date. Time to first event curves will be constructed using Kaplan-Meier estimates and all post procedure results will be summarized with Kaplan-Meier estimates of event rates. Hazard ratios, confidence interval for the hazard ratios, and p-values may also be presented from a Cox proportional hazards model.
- For selected variables, in addition to descriptive summary statistics at each follow-up assessment, change from baseline to subsequent time point will be summarized. Paired (i.e., patients with available data at both baseline and respective time point) and unpaired data will be presented separately for selected variables. In general, patients with missing baseline or following-up values will be excluded from the analysis unless otherwise specified.

 Edwards	Revision Date: January 22, 2019		Rev	 For Use Only by Affiliates of Edwards Lifesciences	Page 16 of 25

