8.2.2 Clinical and Functional Endpoints and Parameters

All-cause mortality rates at 30 days, 6 months, 1 year, and annually thereafter and corresponding 95% confidence intervals will be computed using the Kaplan-Meier algorithm with the standard errors being computed using Greenwood's formula.

Heart failure re-hospitalization rates at 30 days, 6 months, 1 year, and annually thereafter will be summarized with counts and percentages.

Re-intervention rates for tricuspid regurgitation at 30 days, 6 months, 1 year and annually thereafter will be summarized with counts and percentages.

Composite of major adverse events (MAE) defined as cardiovascular mortality, MI, stroke, renal complications requiring unplanned dialysis or renal replacement therapy, severe bleeding, unplanned or emergency re-intervention (either percutaneous or surgical) related to the device and major access site and vascular complications requiring intervention at 6 months, 1 year and annually thereafter will be summarized with counts and percentages.

 Edwards	Revision Date: January 22, 2019		Rev	For Use Only by Affiliates of Edwards Lifesciences	Page 23 of 25
	Title		Statistical Analysis Plan for Edwards CLASP TR EFS		

Change from baseline in NYHA Functional Classification and Edema assessment at 30 days, 6 months, 1 year and annually thereafter will be presented as shift from baseline for each of the pre-specified follow-up periods. Patients that are missing a baseline or follow-up values will be excluded from the paired analysis.

Change from baseline in Quality of Life (QoL) score, as measured by Kansas City Cardiomyopathy Questionnaire (KCCQ), Short Form Health Survey (SF-36) and six minute walk test (6MWT) as well as weight, ankle circumference measurement and patient edema questionnaire at 30 days, 6 months and corresponding follow-up visits will be summarized by mean and standard deviation. Patients that are missing a baseline or follow up values will be excluded from the analysis. For the analyses of 6MWT, patients unable to perform the walk due to a medical reason will be considered to have walked an actual distance of zero. eDiary assessments and Activity Monitoring will be summarized using descriptive statistics based on data types and for each pre-specified follow-up periods.

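### With no common cut-off or vital-status check behind the last-information-date censoring rule, interim Kaplan-Meier mortality is biased upward, mainly at 2 years and later

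*SAP*

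**What the plan says.** SAP 5.1.3 defines the last information date as "the latest date assessed with any available information concerning the patient". It gives as examples the "most recent date out of: baseline assessment, procedure, discharge, all follow-up visits, laboratory tests, and adverse events", and ends: "Last information date is used as the censor date for survival analyses".

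SAP 6.1 treats two groups of event-free patients differently. If the event-free date lies beyond the analysis time point, "the days to event variable will be set equal to the analysis time point". Patients with neither an event nor early withdrawal who "have not yet completed the analysis visit, they will be censored at their last information date".

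SAP 8.2.2 reports all-cause mortality at 30 days, 6 months, 1 year and yearly; the rates and "corresponding 95% confidence intervals will be computed using the Kaplan-Meier algorithm" with Greenwood standard errors.

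Deaths become known by another route. Death is a serious adverse event outcome (Protocol 11.1.2), and Protocol 11.2 says: "The Investigator will report all adverse events to the Sponsor as soon as possible, but no later than 10 working days" after learning of the event. For patients lost or withdrawn early, Protocol 7.4 adds that the "Sponsor may request the site to search the Social Security Death Index and/or other death registries".

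Follow-up visits are at 30 days, 6 months, 1 year and then yearly to 5 years (Protocol 8.11). The eDiary runs one week in two up to the 12-month visit, with one final week from then. Activity monitoring also ends at 12 months. Patients enrolled before system launch need not take part in either (Protocol 5.3.2).

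**The concern.** Kaplan-Meier needs the censoring date to be unrelated to the outcome. Here it may not be. Take two patients last seen at their 1-year visit, both 20 months after implant when the data are analysed. If one died at month 18, the site reports it and the death is an event at month 18. If the other is alive with no new record, follow-up stops at month 12. The death in the gap enters the numerator, while survivors' time in the same gap leaves the risk set. The error runs one way, upward.

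SAP 6.1 expressly covers patients who have not reached the analysis visit, so reporting at incomplete time points is foreseen. This is a single-arm study, so no comparator shares the error, and one stated objective is to guide the design of later studies. An inflated 2-year mortality would carry into their planning assumptions.

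**Working it through.** The documents give no mortality rate, event count or cut-off date, so there is no planned figure to reproduce. Visit days and windows come from the documents; hazard, accrual and analysis date are assumptions, shown as ranges.

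**Two-year estimate by hand.** Assume entry uniform over 18 months, last patient at 1.25 years, constant hazard λ, visits on the nominal day and no other contact.

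1. Possible follow-up c is uniform from 1.25 to 2.75 years. The share with c ≥ 2 is 0.75/1.5 = 50%.
2. Everyone has passed year 1, so the first year contributes λ, as it should.
3. Between years 1 and 2, survivors with c < 2 are censored at their 1-year visit. The risk set is about 50% of those alive.
4. Deaths at time t still come from everyone with c > t: 100% up to 1.25 years, then (2.75 − t)/1.5.
5. The apparent hazard is about λ × P(c > t)/0.5. Over year 2 it sums to λ × [0.25 × 2 + (1.5² − 0.75²)/(2 × 0.75)] = λ × (0.5 + 1.125) = 1.625λ, where it should be λ.
6. Estimated mortality is about 1 − exp(−2.625λ); the truth is 1 − exp(−2λ).

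| λ per year | True | Hand result | Simulated, N = 65 | With one AE contact per year |
|---|---|---|---|---|
| 0.05 | 9.5% | 12.3% | 12.2% | about 11% |
| 0.10 | 18.1% | 23.1% | 22.7% | about 21% |
| 0.15 | 25.9% | 32.5% | 31.9% | about 30% |

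The hand result is slightly high because patients who die in the gap stay in the risk set until death.

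**One-year estimate.** A separate simulation used the SAP 5.2 windows, entry over 540 days and true 1-year mortality of 10 / 15 / 20%.

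| Share past 1 year | Last visit only | Plus one AE or lab contact a year | eDiary days count |
|---|---|---|---|
| about 33% | 13.7 / 20.1 / 26.5% | 12.8 / 18.9 / 24.9% | 10.1 / 14.9 / 20.1% |
| about 66% | 11.5 / 17.2 / 23.2% | 11.3 / 16.9 / 22.2% | 10.0 / 15.1 / 20.2% |
| all | 10.2 / 15.1 / 20.3% | 10.2 / 15.1 / 20.1% | 10.0 / 15.0 / 19.8% |

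The inflation hardly depends on sample size. At a true 15% with a third complete, the mean excess over censoring at the cut is 5.2 points for 65 patients (Protocol) and 5.1 for 15 (SAP).

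**Other time points, same simulation.**
- 2 years, true 19.0%: last-visit censoring gives 27.1% with 31% complete and 22.4% with 65% complete. Counting eDiary days gives 26.8% and 22.4%, so it does not help here. With all complete the estimate is 19.1%.
- 30 days, 89% complete: 0.9% against a true 0.9%, and 2.0% against a true 1.8%.

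**Common cut-off.** When survivors are censored at the date through which deaths are counted, the 1-year estimates are 9.8 / 15.1 / 20.0% with a third complete and 10.0 / 15.0 / 20.1% with two thirds complete. These match the truth within simulation error.

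**Registry deaths.** Assume 20% lost by 5 years, a hazard of 0.10, registry deaths counted and no-match patients left at their last visit. Five-year mortality is then 42.8% against a true 39.3%.

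**The case against.** A reader might infer that the SAP censors survivors at their last visit, counts deaths to the data cut, and so inflates mortality at any incomplete time point. The documents do not support that in full.

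- The rule is the latest information of any kind. The sources in 5.1.3 are examples, so the list is open; eDiary entries, activity data or a registry no-match are not excluded. This stands. If eDiary days count, the year-1 bias almost vanishes for patients who have the eDiary. It does not help patients enrolled before launch, or anyone after year 1.
- No cut-off is defined and no rule says which deaths count. Protocol 11.2 is a reporting deadline, and the registry search is optional. This stands too: the fault is a missing rule. But as nothing excludes a recorded death, counting all of them is the natural reading.
- Patients with information past the time point are truncated there, so they carry no asymmetry. Bias is negligible at 30 days and about 0.1 to 0.3 points once everyone has passed the time point.
- Consequences are limited. Analyses are descriptive, the safety endpoint is 30-day MAE without a hypothesis test, and no decision rule uses interim 2-year mortality.

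These points narrow the scope and size. They do not remove the bias at 2 years and later, where the plan offers no regular contact between annual visits.

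**Conclusion.** The concern holds in limited form. Followed as written, SAP 5.1.3 and 6.1 bias Kaplan-Meier all-cause mortality upward when it is reported before all patients have passed the time point, because the rule for survivors is not matched by any rule for deaths. In the 2-year scenario the excess is about 3 to 6 points. At 1 year it ranges from almost nothing, if eDiary days count for everyone, to about 1.5 to 6.5 points under last-visit censoring with one third to two thirds of patients complete and a true mortality of 10% to 20%. Extra AE or lab contacts reduce it without removing it. Apart from registry-found deaths in lost or withdrawn patients, it essentially disappears once the time point is complete. All sizes rest on assumed hazards, accrual and analysis dates; the direction does not. No test or error rate is affected. The SAP should be corrected before interim mortality at 1 year or later is reported.

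**What to change.** Replace the last sentence of SAP 5.1.3 so that each survival analysis has one stated data cut-off, vital status is confirmed for every patient at that date, and the same date limits both deaths and survivors' follow-up. Align the sentence in 6.1 on patients who have not reached the analysis visit. Where vital status cannot be confirmed, report a time point only after the last patient's visit window has closed. State that eDiary and activity-monitor dates count as information. Where a death registry is searched, censor no-match patients at the date to which the registry is complete.

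Ending everyone's follow-up at the last nominal due visit is a weaker alternative. With the ±45-day windows some due visits have not yet happened, and the 2-year scenario still gives 10.0 / 19.2 / 27.0% against 9.5 / 18.1 / 25.9%. It also leaves known deaths out of an interim report.

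The cost is one derived date plus a vital-status check at each cut, or later reporting of the time point. The SAP needs revision in any case: it is written for protocol version A and 15 patients, while the protocol is version C with up to 65.
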